### **7.2.1. Treatment-Emergent Adverse Events**

TEAEs will be summarized by SOC and PT for each treatment. In addition, a presentation of TEAE preferred terms in decreasing frequency in the GLWL-01 treatment arm will be provided.

### **7.2.2. Treatment-Related Treatment-Emergent Adverse Events**

Every AE will be assessed by the investigator for its relationship to the randomly assigned study medication. The subset of TEAEs considered by the investigator as possibly or probably related to study treatment will be called treatment-related TEAEs. In addition, TEAEs that are missing the investigator assessment for relatedness will be considered treatment-related TEAEs.

Treatment-related TEAEs will be summarized by SOC and PT for each treatment.

### **7.2.3. Serious Treatment-Emergent Adverse Events**

Serious TEAEs and treatment-related SAEs will be summarized by SOC and PT. A separate listing of all SAEs will also be provided.

### **7.2.4. Treatment-Emergent Adverse Events Resulting in Death**

If there are any TEAEs that result in death, a listing of all deaths will be provided.

### **7.2.5. Treatment-Emergent Adverse Events Leading to Study Drug Discontinuation**

For every AE in the eCRF, the investigator indicates whether the action taken with respect to the study drug was dose not changed, dose interrupted, or drug withdrawn.

The TEAEs leading to study drug discontinuation will be summarized for each treatment arm by SOC and PT and by decreasing frequency in the GLWL-01 arm. A separate listing of all TEAEs leading to study drug discontinuation will also be provided.

### **7.2.6. Treatment-Emergent Adverse Events by Maximal Severity**

Every AE will be graded by the investigator as mild, moderate, or severe, so for each patient the greatest severity observed can be obtained by comparing the severity of all of a patient's TEAEs that share the same SOC or PT. A table of TEAEs by maximal severity will be prepared for each treatment arm by SOC and PT.

### **7.3. Clinical Laboratory Summaries**

Blood samples for hematology and serum chemistry will be collected during screening; on Treatment Phase Day 0 (i.e. Baseline) and Treatment Phase Day 28 of each treatment phase; and at a patient's early termination visit, if applicable.

Each laboratory parameter will be classified as low, normal or high relative to the central laboratory's normal range. For each treatment group, shift tables will be generated from the pre-dose category to the category post-dose for each laboratory parameter. The shift tables will present the number (percent) of patients who started in a category (low, normal, high) at baseline and ended in a category at each post-baseline scheduled visit and for the last assessment (including unscheduled and early termination assessments) for each treatment.

Shift tables comparing baseline to the other time points in the study may be generated if warranted after data review.

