Period	Screening ^a	Treatment Period 1				Washout (28 days)	Treatment Period 2			Follow-up	ET ^c	
Phase		Single-blind Placebo Lead-in Phase (14 days)	Double-blind Treatment Phase (28 days) ^b				Single-blind Placebo Lead-in (14 days)	Double-blind Treatment Phase (28 days) ^b				
Visit No/ Type Procedure	V1	V2 ^e Phone	V3 ^d	V4	V5	V6 ^e Phone	V7 ^e Phone	V8	V9	V10	V11	
Day	-28 to -3	0 (±3)	14 (±2)	21 (±2)	42 (±2)	56 (±2)	70 (±2)	84 (±2)	91 (±2)	112 (±2)	126 (±3)	
12-lead ECG ^k	X		X	X	X			X	X	X	X	X
12-lead ECG 2 hours post-dose ^k			X					X				
Serum pregnancy test ^l	X									X		X
Urine pregnancy test ^l			X					X				
Clinical chemistry and hematology ^h	X		X	X	X			X	X	X		X
Troponin			X	X	X			X	X	X		
Lipid panel			X		X			X		X		X
AG and UAG ^m			X		X			X		X		X
Plasma sample collection for PK analysis ⁿ			X		X							X
C-SSRS	X	X	X	X	X	X	X	X	X	X	X	X
Adverse events	X	X	X	X	X	X	X	X	X	X	X	X

Abbreviations: AE = adverse event; AG = acylated-ghrelin; BMI = body mass index; CGIC = Caregiver Global Impression of Change; C-SSRS = Columbia–Suicide Severity Rating Scale; ECG = electrocardiogram; EDC = electronic data capture; ET = early termination; HQ-CT = Hyperphagia Questionnaire for Clinical Trials; HBsAg = hepatitis B surface antigen; HCAB = hepatitis C antibody; HIV = human immunodeficiency virus; PK = pharmacokinetic; UAG = unacylated-ghrelin; V = Visit.

^a Screening visit must occur between -28 days to -3 days of V2.

^b Double-blind Treatment Phase must not exceed 28 days and patients must not take the study drug beyond 28 days. For example, if the V3 occurs on Day 14, then corresponding V5 would occur on Day 42. Similarly, if V3 occurs on Day 15 (Day 14 +1), then corresponding V5 would occur on Day 43 (Day 42 +1).

^c The primary reason for early termination of the patient will be entered in EDC and recorded in the patient's source documents. The patient will attend an early termination visit as soon as possible after participation ceases.

^d Confirm that the patient has met all inclusion/exclusion criteria. Patients will only be dosed after the investigator has completed the appropriate protocol assessments and determined that it is acceptable to dose the patient.

^e Patients/caregivers will receive phone calls from the site; no visit required. Both patient and caregiver should be on the phone in order for the site to conduct AE assessments and the C-SSRS.

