- A clinically significant systemic hypersensitive reaction occurs following administration of the study drug (e.g., study drug-related symptomatic bronchospasm, allergy-related edema/angioedema, or hypotension), that requires parenteral medication, does not respond to symptomatic medication, or result in clinical sequelae or an anaphylactic reaction.
- An elevated troponin I level (greater than 0.04 ng/mL); the patient must be referred for further evaluation.

- Patient has stopped eating or drinking for more than 24 hours.
- Requirement of prohibited concomitant medication.
- Patient failure to comply with protocol requirements or study-related procedures.
- Termination of the study by the sponsor or regulatory authorities.

The clinical report will include reason(s) for patient withdrawals as well as details relevant to the patient withdrawal.

Patient discontinuing from the study prematurely for any reason should complete AE and other follow-up procedures per Section 2 (Schedule of Activities), Section 9.2 (Adverse Events), and Section 9.4 (Safety) of this protocol.

A patient will be considered lost to follow-up if he or she repeatedly fails to return for scheduled visits and is unable to be contacted by the study site. Site personnel are expected to make diligent attempts to contact patients who fail to return for a scheduled visit or were otherwise unable to be followed up by the site.

9. Study Assessments and Procedures

Section 2 lists the Schedule of Activities, with the study procedures and their timing (including tolerance limits for timing).

[Appendix 2](#) lists the laboratory tests that will be performed for this study.

[Appendix 5](#) provides a summary of the maximum number and volume of invasive samples, for all sampling, during the study.

Unless otherwise stated in the subsections below, all samples collected for specified laboratory tests will be destroyed within 60 days of receipt of confirmed test results. Certain samples may be retained for a longer period, if necessary, to comply with applicable laws, regulations, or laboratory certification standards.

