Patients will be defined as having a treatment-emergent low value if they have all normal or high values at baseline, followed by a value below the lower reference limit at any postbaseline visit. Patients with all normal or high values at baseline (no low values) will be included in the analysis of treatment-emergent low laboratory values. Patients will be defined as having a treatment-emergent high value if they have all normal or low values at baseline, followed by a value above the upper reference limit at any postbaseline visit. Patients with all normal or low values at baseline (no high values) will be included in the analysis of treatment-emergent high laboratory values.

For analytes simply classified as normal or abnormal, patients will be defined as having a treatment-emergent abnormal value if they have all normal values at baseline, followed by an abnormal value at any postbaseline visit. Patients with all normal values at baseline will be included in the analysis of treatment-emergent abnormal laboratory values.

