 - total bilirubin level (TBL) >2X ULN or
 - prothrombin time >1.5X ULN or
 - the appearance of fatigue, nausea, vomiting, right upper-quadrant pain or tenderness, fever, rash, and/or eosinophilia (>5%)
- ALP >3X ULN
- ALP >2.5X ULN and TBL >2X ULN
- ALP >2.5X ULN with the appearance of fatigue, nausea, vomiting, right upper-quadrant pain or tenderness, fever, rash, and/or eosinophilia (>5%)
- Marked prolongation of the QT/QTc interval >500 ms or >60 ms over baseline, judged medically significant following repeat ECG after 5 minutes of rest from the initial ECG.
- A clinically significant systemic hypersensitive reaction occurs following administration of the study drug (e.g., study drug-related symptomatic bronchospasm, allergy-related edema/angioedema, or hypotension), that requires parenteral medication, does not respond to symptomatic medication, or result in clinical sequelae or an anaphylactic reaction.
- Requirement of prohibited concomitant medication.
- Patient failure to comply with protocol requirements or study-related procedures.

- Termination of the study by the sponsor or regulatory authorities.

The clinical report will include reason(s) for patient withdrawals as well as details relevant to the patient withdrawal.

Patient discontinuing from the study prematurely for any reason should complete AE and other follow-up procedures per Section 2 (Schedule of Activities), Section 9.2 (Adverse Events), and Section 9.4 (Safety) of this protocol.

A patient will be considered lost to follow-up if he or she repeatedly fails to return for scheduled visits and is unable to be contacted by the study site. Site personnel are expected to make diligent attempts to contact patients who fail to return for a scheduled visit or were otherwise unable to be followed up by the site.

**Appendix 7. Protocol Amendment GLWL-PWS(b)
Summary [A Phase 2 Study to Evaluate Efficacy, Safety,
and Pharmacokinetics of GLWL-01 in the Treatment of
Patients with Prader-Willi Syndrome]**

Overview

Protocol GLWL-PWS [A Phase 2 Study to Evaluate Efficacy, Safety, and Pharmacokinetics of GLWL-01 in the Treatment of Patients with Prader-Willi Syndrome] has been amended. The new protocol is indicated by amendment (b) and will be used to conduct the study in place of any preceding version of the protocol.

The overall changes and rationale for the changes made to this protocol are as follows:

- Troponin I testing has been added to Visits 3, 4, 5, 8, 9, and 10 as requested by FDA

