- ECGs 2 hours post-dose have been added at Visits 3 and 8 as requested by FDA
- ECGs have been added to Visits 4 and 9 as requested by FDA
- Visit 4 occurs on Day 21 and visit 9 occurs on Day 91 as requested by FDA
- Visits 2 and 7 will be phone visits due to change of Visits 4 and 9 to in-person visits
- The following discontinuation criteria have been added as requested by FDA:
 - Patients with elevated troponin I level (greater than 0.04 ng/mL) must be withdrawn from the study. Elevations must be referred for further evaluation.
 - Patients who have stopped eating or drinking for more than 24 hours must be withdrawn from the study.
- Minor textual edits were made for the purpose of clarification or correction.

Revised Protocol Sections

Note: Deletions have been identified by ~~strikethroughs~~ or grayed out for figures.
Additions have been identified by the use of underscore.

1. Synopsis

Title of Study:

A Phase 2 Study to Evaluate Efficacy, Safety, and Pharmacokinetics of GLWL-01 in the Treatment of Patients with Prader-Willi Syndrome (PWS)

Rationale:

The aim of this study is to evaluate efficacy, safety, and pharmacokinetics of GLWL-01 in the treatment of patients with Prader-Willi Syndrome (PWS).

Objectives/Endpoints:

Objectives	Endpoints

Primary
 
 Evaluate the efficacy of GLWL-01 compared with placebo in reducing hyperphagia-related behaviors after 28 days of treatment in patients with PWS as measured using the Hyperphagia Questionnaire for Clinical Trials (HQ-CT) 	
 Posttreatment HQ-CT total score

Secondary
 
 Evaluate the safety and tolerability of GLWL-01 after 28 days of treatment in patients with PWS Evaluate the efficacy of GLWL-01 compared with placebo in reducing hyperphagia-related behaviors after 28 days of treatment in patients with PWS as measured using the Caregiver Global Impression of Change (CGIC) Evaluate the pharmacokinetics after single and multiple oral dosing of GLWL-01 in patients with PWS 	
 Treatment-emergent adverse events CGIC score GLWL-01 
 Area under the concentration versus time curve from time zero to 12 hours (AUC₀₋₁₂) Maximum observed drug concentration (C_{max})

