### **7.5. Electrocardiogram Summaries**

Single 12-lead electrocardiograms (ECGs) will be assessed during screening; on Treatment Phase Day 0 (i.e. Baseline), Treatment Phase Day 7, and Treatment Phase Day 28 of each treatment phase; and at a patient's early termination visit, if applicable. Two-hour post-dose ECG assessments will also be made at Baseline of each treatment phase.

The number and percent of patients with any post-baseline Fridericia-corrected QT values of potential clinical interest (including unscheduled and early termination assessments) will be summarized. QTcF values of potential clinical interest will be determined using the following criteria:

- QTcF  $\geq$  480 msec, or  $\geq$  500 msec, or  $\geq$  550 msec
- Change from baseline in QTcF  $\geq$  30 msec, or  $\geq$  60 msec.

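### SAP 7.3 leaves the Day 7 laboratory draws off its list and drops, without declaring it, the protocol's patient-level count of abnormal values at any time after baseline

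*SAP*

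**What the plan says.** SAP 7.3 places the laboratory draws at screening, then "on Treatment Phase Day 0 (i.e. Baseline) and Treatment Phase Day 28 of each treatment phase", then at early termination where that applies. It commits to low/normal/high shift tables against the central laboratory's range, from baseline to every scheduled visit after baseline and to the last assessment. Unscheduled and early termination results enter only through that last assessment. Shifts to other time points are optional, to be decided once the data have been reviewed.

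In the protocol's Schedule of Activities, the row "Clinical chemistry and hematology" is marked at Visits 1, 3, 4, 5, 8, 9, 10 and early termination. The troponin row is marked at Visits 3, 4, 5, 8, 9 and 10. SAP 7.4 and 7.5, which cover vital signs and ECGs at the same visits, list baseline and then "Treatment Phase Day 7, and Treatment Phase Day 28 of each treatment phase".

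Protocol 10.3.4 plans the incidence of patients with treatment-emergent abnormal, high or low results, compared with Fisher's exact test. A treatment-emergent high is no high value at baseline, "followed by a value above the upper reference limit at any postbaseline visit". Low and abnormal are defined in the same way.

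SAP Section 7 plans no statistical analyses of safety endpoints. SAP 2.9 records four changes from the protocol: the population's name, the addition of blood glucose, the treatment-emergent adverse event rule, and 1-sided testing. The laboratory analysis is not among them.

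**The concern.** There are two separate problems.

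The first is the visit list. The SAP states that it is based on protocol amendment (d), whose schedule includes the Visit 4 and Visit 9 draws, yet its laboratory section does not name them. A programmer working from 7.3 alone would build tables for Day 28 only and could treat Day 7 as one of the optional other time points.

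The second is the summary itself. The protocol promised, per patient, whether any value after baseline became abnormal. A set of shift tables answers a different question, namely where patients stood at each visit and at the end. An abnormality that appears and then resolves is what the protocol's count would catch and a last-value shift would not.

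Safety and tolerability is a stated secondary objective, and the laboratory results are part of that assessment. With about 19 patients the safety tables will be read as patient counts, so the lost count matters to the reader of the report even though no test depends on it.

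**Working it through.** No sample size, power or error-rate figure is involved, so there is no figure of the plan's to reproduce. The check compares schedules and then follows possible patients through the tables.

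**Inputs.** Visit days come from the protocol schedule: V4 = 21, V5 = 42, V9 = 91, V10 = 112. Under SAP 2.3, treatment phase day is visit date minus the date of the first double-blind dose, planned for Study Day 14 in the first phase and Study Day 84 in the second. The anticipated number of patients is 19 (SAP 2.9).

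**Step 1: phase days.**

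| Visit | Phase day | Chemistry and hematology in protocol schedule | Named in SAP 7.3 | Named in SAP 7.4 and 7.5 |
|---|---|---|---|---|
| V4 | 21 − 14 = 7 | yes | no | yes |
| V5 | 42 − 14 = 28 | yes | yes | yes |
| V9 | 91 − 84 = 7 | yes | no | yes |
| V10 | 112 − 84 = 28 | yes | yes | yes |

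**Step 2: size.** A patient who completes both phases has 4 scheduled on-treatment draws, and SAP 7.3 names 2. For 19 completers that is 19 × 4 = 76 draws, of which 19 × 2 = 38 (50%) are not named.

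**Step 3: what the tables would show.** Take a patient whose analyte is normal at baseline. The narrow reading takes scheduled visits to mean those that 7.3 lists. The broad reading takes them from the protocol schedule.

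| Pattern after baseline | 7.3, narrow reading | 7.3, broad reading | Protocol 10.3.4 count |
|---|---|---|---|
| High at Day 7, normal at Day 28 (last value) | not shown as high | shown in the Day 7 shift | counted |
| High at an unscheduled draw, normal at both scheduled visits and at the last value | not shown as high | not shown as high | counted |
| High at Day 28 | shown | shown | counted |

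The second row is lost on either reading.

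**Step 4: whether the count can be rebuilt from the shifts.** If *a* patients on a treatment become high at Day 7 and *b* at Day 28, the number high at either visit lies between max(*a*, *b*) and *a* + *b* (capped at the number of patients). The separate tables do not say which value is right, and they omit unscheduled values that are not the last. The any-time count therefore cannot be recovered from the committed shifts.

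**Step 5: how often it could matter (illustration only).** Let *p* be the chance that a patient on GLWL-01 has an abnormality at Day 7 that has resolved by Day 28. The documents give no such rate, so *p* is assumed. With 19 independent patients, the chance of at least one is 1 − (1 − *p*)^19:

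- *p* = 0.02: 32%
- *p* = 0.05: 62%
- *p* = 0.10: 86%
- *p* = 0.20: 99%

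The point does not rest on these values.

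**Step 6: comparison within the SAP.** SAP 7.4 and 7.5 keep a patient count over all post-baseline values, with unscheduled and early termination assessments included, for pulse and blood pressure and for QTcF. Among these three sections, only the laboratory one has no such count.

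**The case against.** The strongest reply is that SAP 7.3 already covers Day 7. Its shift sentence speaks of every scheduled visit after baseline, Visits 4 and 9 are scheduled, and SAP 1.1 sends the reader to the protocol for the schedule. On that view the timing sentence is merely incomplete. This is a fair reading and it stands as a possibility. The section's own list and its optional-time-points sentence point the other way, so the text is ambiguous. The table formats are in a companion document that is not part of this review, and it may settle the matter. Even if it does, Step 3 shows that the unscheduled case and the patient-level count are still missing.

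A reader might infer that Day 7 or transient abnormalities would go unreported. The documents do not support that. The values stay in the datasets. The protocol synopsis says safety parameters will be listed as well as summarized. Under Protocol 9.4.3, clinically significant findings that lead to a diagnosis are reported as adverse events. The gap is in the committed summary tables only.

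A reader might also take troponin as the clearest casualty. It is a weak example:

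- Troponin I is in the chemistry panel in Protocol Appendix 2, so the shifts for each laboratory parameter can include it.
- "An elevated troponin I level (greater than 0.04 ng/mL") is a listed reason for discontinuation in Protocol Section 8. A patient stopped for it would appear in the disposition summary.
- No troponin is scheduled at early termination, so for a patient stopped at Day 7 that value would probably be the last and would appear in the last-assessment shift.
- Protocol 10.3.4 plans no count against 0.04 ng/mL, so the absence of one in the SAP is not a departure from the plan.

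What remains is the patient who continues, or whose repeat is normal, and who would then appear as abnormal in no committed table unless Day 7 shifts are produced.

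It can also be said that this is a small proof-of-concept trial with descriptive safety, where individual values can be read directly. That limits the weight of the point. It does not explain why the laboratory count was removed while the counts for vital signs and QTcF were kept. Finally, Protocol 10.3.1 lets analysis changes be described in the SAP and/or the clinical study report, so silence in SAP 2.9 is not in itself a breach. But 2.9 is where this SAP records its changes, and no reason is given elsewhere in it.

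**Conclusion.** The point holds in two parts. First, SAP 7.3 does not name the Day 7 draws that the protocol schedules, 2 of 4 per completing patient (38 of 76 if all 19 complete both phases). These are draws missing from a list, not draws shown to be excluded from the tables; the result is ambiguity about Day 7 shifts. Second, the protocol's patient-level incidence of treatment-emergent laboratory abnormalities at any time after baseline is gone, on either reading of 7.3, and SAP 2.9 does not say so. SAP Section 7 implies that Fisher's exact test is dropped; nothing in the SAP says that the count is dropped too.

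The stronger conclusion, that transient abnormalities or raised troponin would escape reporting altogether, is not supported. The primary efficacy result and the data collected are unaffected. This is a moderate reporting fault, worth correcting because the correction is small.

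**What to change.** - In SAP 7.3, add Treatment Phase Day 7 to the list of laboratory draws, in line with the protocol schedule and SAP 7.4 and 7.5.
- Restore the Protocol 10.3.4 count: for each laboratory test, the number and percent of patients with a treatment-emergent high, low or abnormal value at any time after baseline, derived within each phase and tabulated by treatment. Include unscheduled and early termination values, and use the protocol's denominators (patients without that abnormality at baseline). Keep it descriptive, consistent with SAP Section 7.
- In SAP 2.9, record that Fisher's exact test is dropped for the laboratory incidences, with the reason. If the sponsor prefers not to restore the count, record and justify that there as well.
- Optionally, list or count troponin I values above the protocol's 0.04 ng/mL criterion by treatment. This would be an addition to the protocol's planned analysis, not a repair of it.

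The cost is a few lines of SAP text and one added table. No new data are needed.

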6.2. Exclusion Criteria

Patients will be excluded from study enrollment if they meet any of the following criteria at screening:

9. Are Eli Lilly and Company, GLWL Research Inc. (sponsor hereafter), contract research organization employees, investigator or site personnel directly affiliated with this study and their immediate families. Immediate family is defined as a spouse, parent, child or sibling, whether biological or legally adopted.
10. Are currently enrolled in any other clinical trial involving a study drug or off-label use of a drug or device, or any other type of medical research judged not to be scientifically or medically compatible with this study.
11. Participated in a clinical trial within 30 days (defined as last dose of study drug), prior to the GLWL-PWS first dose.
12. Are currently living in a group home for more than 50% of the time.
13. Have a HQ-CT total score at Visit 3 <13.
14. Have clinical laboratory test results outside normal reference range, or any clinically significant laboratory abnormality, that in the judgment of the investigator, indicates a medical problem that would preclude study participation. Values for aspartate aminotransferase (AST)/alanine aminotransferase (ALT)/gamma-glutamyl transferase (GGT)/alkaline phosphatase (ALP) >3X upper limit of normal (ULN).
15. Have an estimated glomerular filtration rate <60 mL/minute/1.73 m². Have macroalbuminuria (defined as spot urine albumin to creatinine ratio of >300 µg/mg) or hematuria.
16. Are hypertensive (defined as sitting systolic BP ≥140 mmHg and diastolic BP ≥90 mmHg) on or off medications for the treatment of hypertension. Blood pressure may be re-tested up to 2 additional times, under well-rested conditions.

17. In addition to conditions described below, have a history or presence of any other medical illness including but not limited to any autoimmune disorder, cardiovascular, hepatic, respiratory, hematological, or uncontrolled neurological disease.

- a. Have a history of clinically overt uncontrolled or untreated endocrine illness such as growth hormone insufficiency, adrenal gland, or thyroid illness.

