7.8. Treatment after the End of the Study

Not applicable.

8. Discontinuation Criteria

Patient participation in the study may be discontinued for any of the following reasons:

- Enrollment in any other clinical study involving any study drug or enrollment in any other type of medical research judged not to be scientifically or medically compatible with this study.
- **Investigator's decision:** the investigator decides that the patient should be discontinued from the study.
- **Patient's/caregiver's decision:** the patient or caregiver requests to be discontinued from the study.
- **Sponsor's decision:** GLWL stops the study or stops the patient's participation in the study for medical, safety, regulatory, or other reasons consistent with applicable laws, regulations, and GCP.
- **Adverse event:** any SAE or a significant change in a laboratory value occurs that merits the study drug being discontinued and necessitates appropriate measures being taken. In this case, the sponsor is to be notified immediately.
- **Hepatic event or liver test abnormality:** Patients who are discontinued from using study drug due to a hepatic event or liver test abnormality should have additional hepatic safety data collected via electronic data entry.

Discontinuation of the study drug for abnormal liver test results **should be** considered by the investigator when a patient meets 1 of the following conditions after consultation with the sponsor medical representative:

- ALT or AST >5X ULN
- ALT or AST >3X ULN along with 1 of the following criteria:
 - sustained for more than 2 weeks or
 - total bilirubin level (TBL) >2X ULN or
 - prothrombin time >1.5X ULN or
 - the appearance of fatigue, nausea, vomiting, right upper-quadrant pain or tenderness, fever, rash, and/or eosinophilia (>5%)
- ALP >3X ULN
- ALP >2.5X ULN and TBL >2X ULN
- ALP >2.5X ULN with the appearance of fatigue, nausea, vomiting, right upper-quadrant pain or tenderness, fever, rash, and/or eosinophilia (>5%)
- Marked prolongation of the QT/QTc interval >500 ms or >60 ms over baseline, judged medically significant following repeat ECG after 5 minutes of rest from the initial ECG.

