9.4.5.1. Hepatic Safety Monitoring

If a study patient experiences elevated ALT ≥ 3 X ULN, ALP ≥ 2 X ULN, or elevated TBL ≥ 2 X ULN, liver tests ([Appendix 4](#)) should be repeated within 3 to 5 days including ALT, AST, ALP, TBL, direct bilirubin, gamma-glutamyl transferase, and creatine kinase to confirm the abnormality and to determine if it is increasing or decreasing. If the abnormality persists or worsens, clinical and laboratory monitoring should be initiated by the investigator and in consultation with the study medical monitor. Monitoring of ALT, AST, TBL, and ALP should continue until levels normalize or return to approximate baseline levels.

Hepatic Safety Data Collection

Additional safety data should be collected via the electronic data entry if 1 or more of the following conditions occur:

- elevation of serum ALT to ≥ 5 X ULN on 2 or more consecutive blood tests
- elevation of serum TBL to ≥ 2 X ULN (except for cases of known Gilbert's syndrome)
- elevation of serum ALP to ≥ 2 X ULN on 2 or more consecutive blood tests
- patient discontinued from treatment due to a hepatic event or abnormality of liver tests
- hepatic event considered to be an SAE

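### Liver tests are summarised only as low/normal/high shifts per analyte, so no planned summary counts the protocol's own hepatic limits by treatment

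*SAP*

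**What the plan says.** **Laboratory summary.** SAP Section 7.3 sets three categories: "Each laboratory parameter will be classified as low, normal or high relative to the central laboratory's normal range". From these, "shift tables will be generated from the pre-dose category to the category post-dose for each laboratory parameter". The tables cover each scheduled post-baseline visit and the last assessment. Unscheduled and early-termination results enter only through that last assessment. More shift tables at other time points are optional after data review, on the same three categories.

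**Entry.** Protocol Section 6.2, criterion 14, has a numeric limit: "Values for aspartate aminotransferase (AST)/alanine aminotransferase (ALT)/gamma-glutamyl transferase (GGT)/alkaline phosphatase (ALP) >3X upper limit of normal (ULN". The same criterion also excludes out-of-range results "that in the judgment of the investigator, indicates a medical problem that would preclude study participation". Criterion 17 separately excludes hepatic illness and chronic liver disease.

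**Hepatic limits.** Protocol Section 8 lists liver results that prompt the investigator to consider stopping study drug:
- ALT or AST above 5X ULN;
- "ALT or AST >3X ULN along with 1 of the following criteria", one of which is total bilirubin (TBL) above 2X ULN;
- ALP above 3X ULN;
- ALP above 2.5X ULN with TBL above 2X ULN, or with symptoms.

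Section 9.4.5.1 triggers a retest at ALT ≥3X, ALP ≥2X or TBL ≥2X ULN. It asks for extra hepatic data at, among others, "elevation of serum ALT to ≥ 5 X ULN on 2 or more consecutive blood tests", ALP ≥2X ULN on consecutive tests, and TBL ≥2X ULN.

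**Treatment-emergent high values.** Protocol Section 10.3.4: "Patients with all normal or low values at baseline (no high values) will be included in the analysis of treatment-emergent high laboratory values".

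**Contrast.** SAP Sections 7.4 and 7.5 count patients with any post-baseline vital sign or QTcF value beyond fixed thresholds, unscheduled assessments included.

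**The concern.** The protocol expresses liver safety in multiples of ULN and, in two conditions, as a pair of tests. The SAP summarises it on a scale whose top category begins at 1X ULN and never ends, one test at a time. The limits that the trial acts on and the summary that it reports therefore do not meet.

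Safety and tolerability is a secondary objective, and SAP Section 2.9 anticipates 19 patients. At that size any liver signal is likely to be one or two cases, so the height of each rise is most of the information. A table that gives a trivial rise and a marked one the same entry leaves the by-treatment comparison silent on what matters.

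**Working it through.** The plan states no figure on this point, so there is nothing to reproduce. The check applies the written rules to example values and then looks for any other planned summary that would fill the gap.

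**1. The scale.** Write each value as a multiple of ULN. Under SAP 7.3 a value is high if it exceeds 1. Under protocol 10.3.4 a patient enters the treatment-emergent-high analysis only if baseline is not high.

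| Baseline → post-baseline (X ULN) | SAP 7.3 cell | Protocol 10.3.4 | Above 3X | Above 5X |
|---|---|---|---|---|
| 0.8 → 1.1 | normal to high | counted | no | no |
| 0.8 → 10 | normal to high | counted | yes | yes |
| 1.1 → 10 | high to high | left out | yes | yes |
| 2 → 2.1 | high to high | left out | no | no |
| 2 → 5.1 | high to high | left out | yes | yes |
| 2 → 10 | high to high | left out | yes | yes |
| 3 → 10 | high to high | left out | yes | yes |

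Rows 1 and 2 share a cell, and so do rows 3 to 7. The last two columns, which separate them, correspond to no planned table.

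**2. Where a high baseline can arise.** Criterion 14 leaves 1X to 3X ULN open to entry, subject to judgment and criterion 17. It applies at screening, whereas SAP Section 2.3 takes the last pre-dose value of each phase as baseline. The affected unit is therefore one analyte in one phase.

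**3. Timing.** A patient at 10X ULN on an unscheduled draw who is back at 1X by the last assessment appears in no shift table at 10X. SAP 7.3 names Treatment Phase Days 0 and 28. The Schedule of Activities also has chemistry at Visits 4 and 9, which is phase Day 7 (21 − 14 and 91 − 84). Adding that visit would not help with step 1, because the scale is the same.

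**4. Pairing.** Each analyte has its own table. A patient with ALT above 3X and TBL above 2X ULN contributes one entry to each, and nothing links the two.

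**5. Other routes.**
- *Adverse events.* Protocol Section 9.4.3 asks for a laboratory finding to be reported when it is clinically significant and leads to a diagnosis, so a symptom-free enzyme rise need not become an AE. The severity scale in Section 9.2 rests on disruption of daily activities, not on the laboratory value.
- *Discontinuations.* SAP Section 7.2.5 tabulates TEAEs that lead to withdrawal of drug, but protocol Section 8 makes stopping for liver tests a matter for consideration. Withdrawals do not count crossings.
- *Descriptive statistics.* The protocol synopsis and SAP Section 2.8 mention them in general; SAP 7.3 does not call for them. A mean or maximum gives neither a count of patients over a limit nor a pairing.
- *Protocol 10.3.4.* It also cuts at 1X ULN, omits baseline-high patients, and is not carried into SAP 7.3.

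**6. How few cases to expect (illustration only).** Neither document gives a rate of limit crossings. If all 19 patients receive GLWL-01 and the per-patient rate is *p*, the chance of at least one case is 1 − (1 − *p*)^19: 17% at *p* = 1%, 62% at 5%, 87% at 10%. Zero cases in 19 gives a one-sided 95% upper bound of 1 − 0.05^(1/19) = 14.6%. Any count would be small, so the size of each rise matters.

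**The case against.** The best opposing case is that the trial would not miss serious liver injury. TEAEs, serious TEAEs, TEAEs leading to discontinuation and TEAEs by maximal severity are all tabulated by treatment, and TEAEs are the named endpoint of the safety objective. Individual values are in the datasets, and with about 19 patients a listing would let a reader find a 10X value or a raised transaminase beside a raised bilirubin. The Section 8 limits guide the care of one patient; no document says they must be tabulated. The protocol's benefit/risk section reports no clinically significant safety concern to date, and SAP Section 1.1 allows supportive analyses to be added without amendment.

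Much of this stands, and it rules out three stronger readings that a reader might infer:
- *That hepatic worsening in baseline-high patients would be invisible.* It would not: the AE tables and listings may show it. What is lost is its distinction in the laboratory shift table.
- *That some number of patients cannot show worsening.* The documents give no share entering above ULN. A patient with high ALT can still shift on AST, ALP or bilirubin, and baseline is reset for the second phase. No patient count should be put on this.
- *That anyone up to 3X ULN simply enters, or that the Section 8 limits are automatic stopping rules.* Entry is subject to investigator judgment and criterion 17, and the limits prompt consideration.

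What does not stand is that these routes replace a count. They depend on investigator reporting or on reading listings patient by patient. An analysis added after unblinding is weaker than one fixed beforehand.

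**Conclusion.** The point holds as a gap in reporting. On the SAP 7.3 scale, further worsening of an analyte that is high at a phase's baseline cannot be distinguished in that phase's shift table. Rises from a normal baseline lose their size, unscheduled peaks can drop out, and paired abnormalities are not shown. The number of planned summaries that count the protocol's hepatic limits by treatment is zero.

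This rests on the written rules alone and on no assumed rate or baseline prevalence. It does not show that hepatotoxicity would go undetected. It is a modest weakness that is cheap to repair, and the SAP already uses the better method for vital signs and QTcF.

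**What to change.** Add one table to SAP Section 7.3. By treatment (each double-blind phase with its reporting period to 14 days after the last dose, as in SAP Section 2.3.1), give the number and percent of Evaluable patients with any post-baseline value crossing the multiples already in protocol Sections 8 and 9.4.5.1:
- ALT ≥3X ULN;
- ALT or AST >3X and >5X ULN;
- ALP ≥2X, >2.5X and >3X ULN;
- TBL ≥2X ULN;
- ALT or AST >3X with TBL >2X ULN, and ALP >2.5X with TBL >2X ULN.

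Count separately the patients who meet the consecutive-test conditions of Section 9.4.5.1 (ALT ≥5X, ALP ≥2X ULN). Include unscheduled, early-termination and any local-laboratory results, since Appendix 4 lets hepatic monitoring tests be run locally and those may hold the peak. State whether the two values of a combined condition must come from one sample.

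Keep every patient in the denominator whatever the baseline. For each patient who crosses a limit, list the baseline and peak multiples; a cross-tabulation by baseline band would be mostly empty.

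This is a reporting rule and changes no clinical limit. It needs no new visits or samples. The costs are one extra table with sparse cells at about 19 patients, and making sure any local retest results and their reference ranges reach the database.
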